Appendix C Handling of Human Biological Samples

C 1 Chain of Custody

A full chain of custody is maintained for all samples throughout their lifecycle.

The Investigator at each site keeps full traceability of collected biological samples from the participants while in storage at the center until shipment or disposal (where appropriate) and records relevant processing information related to the samples while at the site.

The sample receiver keeps full traceability of the samples while in storage and during use until used or disposed of or until further shipment, and keeps record of receipt of arrival and onward shipment or disposal.

The Sponsor or delegated representatives will keep oversight of the entire life cycle through internal procedures, monitoring of study sites, auditing or process checks, and contractual requirements of external laboratory providers

Samples retained for further use will be stored in the Sponsor-assigned biobanks or other sample archive facilities and will be tracked by the appropriate Sponsor team for the remainder of the sample life cycle.

All appropriately consented samples will be retained for maximum 15 years from last subject last visit.

If required, the Sponsor will ensure that remaining biological samples are returned to the site according to local regulations or at the end of the retention period, whichever is the sooner.

C 2 Withdrawal of Informed Consent for Donated Biological Samples

The Sponsor ensures that biological samples are returned to the source or destroyed at the end of a specified period as described in the informed consent.

If a participant withdraws consent to the use of donated biological samples, the samples will be disposed of/destroyed/repatriated, and the action documented. If samples are already analysed, the Sponsor is not obliged to destroy the results of this research.

Following withdrawal of consent for biological samples, further study participation should be considered in relation to the withdrawal processes outlined in the informed consent.

The Investigator:

Ensures the participant's withdrawal of informed consent to the use of donated samples is highlighted immediately to the Sponsor or delegate.

Ensures that relevant human biological samples from that participant, if stored at the study site, are immediately identified, disposed of as appropriate, and the action documented.

Ensures that the participant and the Sponsor are informed about the sample disposal.

The Sponsor ensures the organization(s) holding the samples is/are informed about the withdrawn consent immediately and that samples are disposed of or repatriated as appropriate, and the action is documented, and study site is notified.

C 3 International Air Transport Association Guidance Document 62nd edition

LABELLING AND SHIPMENT OF BIOHAZARD SAMPLES

The International Air Transport Association (IATA) (<https://www.iata.org/whatwedo/cargo/dgr/Pages/download.aspx>) classifies infectious substances into three categories: Category A, Category B, or Exempt

Category A Infectious Substances are infectious substances in a form that, when exposure to it occurs, is capable of causing permanent disability, life-threatening or fatal disease in otherwise healthy humans or animals.

Category A Pathogens are, eg, Ebola, Lassa fever virus. Infectious substances meeting these criteria which cause disease in humans or both in humans and animals must be assigned to UN 2814. Infectious substances which cause disease only in animals must be assigned to UN 2900.

Category B Infectious Substances are infectious substances that do not meet the criteria for inclusion in Category A. Category B pathogens are, eg, Hepatitis A, C, D, and E viruses. They are assigned the following UN number and proper shipping name:

UN 3373 – Biological Substance, Category B

Are to be packed in accordance with UN 3373 and IATA 650

Exempt Substances are substances which do not contain infectious substances, or substances which are unlikely to cause disease in humans or animals, are not subject to these regulations unless they meet the criteria for inclusion in another class.

Clinical study samples will fall into Category B or exempt under IATA regulations.

Clinical study samples will routinely be packed and transported at ambient temperature in IATA 650 compliant packaging (<https://www.iata.org/contentassets/b08040a138dc4442a4f066e6fb99fe2a/dgr-62-en-650.pdf>).

Biological samples transported in dry ice require additional dangerous goods specification for the dry ice content.

Appendix D Protocol Version History

The Summary of Changes Table for the current revision is located directly before the Table of Contents.

CSP Version 2.0: (11 April 2024)

Overall Rationale for the Modification

The main purpose of this protocol modification is to expand on the AESI definition for RSV vaccines and to clarify the collection of prohibited medications and vaccinations.

Summary of Changes:

List of Substantial Modifications

Section Number and Name	Description of Change	Brief Rationale
Section 8.4.7 (Adverse Events of Special Interest)	Updated to specify that AESIs will include additional immune-mediated neurological disease and atrial fibrillation	To ensure robust assessment of safety

List of Non-Substantial Modifications

Section Number and Name	Description of Change	Brief Rationale
Section 1.3 (Schedule of Activities)	Inclusion of height and weight measurement at Visit 1 (pre-dose)	To calculate BMI
	Footnote d updated to indicate that prohibited medications will be recorded in the eCRF	Minor update to align more closely with the ICF – clarification that prohibited medications will be recorded in the eCRF and not just in the source documents
Section 6.9 (Prior and Concomitant Medications)	Restricted medications' changed to 'prohibited medications'	Updated for clarity
Section 8.3.2 (Vital Signs)	Height and weight measurements added to the list of parameters assessed as part of vital signs	To calculate BMI
Section 8.4.12 (Medication Error and Study Intervention Misuse)	Title updated from 'Drug Abuse and Drug Misuse' to 'Study Intervention Misuse'	Updated for clarity
Appendix D (Protocol Version History)	Added	Added to reflect this amendment to the protocol

REFERENCES

Branche et al 2022

Colosia et al 2017

Falsey et al 2005

List abbreviations and definitions of specialized or unusual terms, measurements, or units. Examples are provided below. These can be modified at study level.

Abbreviation or Specialized Term	Definition
AE	Adverse event
AESI	Adverse Event of Special Interest
AR	Adverse Reaction
ANCOVA	Analysis of Covariance
ATC	Anatomic Therapeutic Chemical
BMI	Body Mass Index
CDL	Clinical Database Lock
CI	Confidence Interval
CRF	Case Report Form
CSP	Clinical Study Protocol
CSR	Clinical Study Report
CTMS	Clinical Trial Management System
ECG	Electrocardiogram
GMC	Geometric Mean Concentration
GMT	Geometric Mean Titer
GMFR	Geometric Mean Fold Rise
hMPV	Human Metapneumovirus
IAS	Immunogenicity Analysis Set
IP	Investigational Product
IPD	Important Protocol Deviation
IRT	Interactive Response Technology
IV	Intravenous
LLoQ	Lower Limit of Quantification
MAAE	Medically-attended Adverse Events
MedDRA	Medical Dictionary for Regulatory Activities
MI	Multiple Imputation
MMRM	Mixed Model for Repeated Measurements
nAb	Neutralizing Antibody
PD	Protocol Deviation
PDNC	Protocol Deviation and Non-compliance
PT	Preferred Term

Abbreviation or Specialized Term	Definition
RSV	Respiratory Syncytial Virus
SAE	Serious Adverse Event
SAF	Safety Analysis Set
SAP	Statistical Analysis Plan
SIP	Study Integrity Plan
SOC	System Organ Class
ULoQ	Upper Limit of Quantification
VLP	Virus-like Particle

AMENDMENT HISTORY

Category Change refers to:	Date	Description of change	In line with CSP?	Rationale
N/A	26 June 2024	Initial approved SAP	N/A	N/A
First amendment to SAP	27 Aug 2024	
1 General update: “Arm” changed to “group”
 
2 Table 2 and Section 2: clarified description of Immunogenicity analysis set in Table 2 and added note in Section 2 regarding this change
 
3 Sections 3.2, Section 4.2.1.7, and Table 5: removed MN RSV A assay from primary analysis
 
4 Section 3.4: added language for presentation of CIs for subgroup analyses with small sample size
 
5 Sections 3.4.1 and 4.2.1.8: added definition of Baseline Tertiles to Sections 3.4.1 and 4.2.1.8
 
6 Section 4.1.11.1: further divided partially compliant (1-7 days completed) into partially compliant (6-7 days completed) and poorly compliant (1-5 days completed)
 
7 Section 4.6.2.1: removed language related to imputation of missing AE severity or AE relationship, and updated rules for summarizing AEs with missing intensity or missing relationship
 
8 Section 4.6.2.1: clarified calculation of duration for solicited ARs with missing stop dates
 
9 Section 4.6.2.2: changed threshold of duration for presenting number and percentage of participants who experience an AR from <=3 days to <=4 days
 
10 Section 4.6.2.2: removed statement related to presentation of unsolicited AEs by maximum severity.
 
11 Section 4.6.2.2: included a statement for presentation of unsolicited AEs by decreasing frequency on PT
 
12 Appendix A: added PT codes
 
13 Appendix B: for imputation of missing start day, removed statement related to “AE onset status on day of IP administration field”
	Yes	
1 Editorial update
 
2 Clarification on the immunogenicity analysis set definition
 
3 Clarification of assays used in primary analyses
 
4 Clarified presentation of CIs in analyses
 
5 Clarification on the calculation of tertiles
 
6 To align with definition of important PD for eDiary completion (i.e. >=3 is an IPD)
 
7 To minimize bias, missing AE severity or missing AE relationship will not be imputed
 
8 Clarification of calculation of duration
 
9 To align with competitor studies
 
10 Summary not needed for interpretation
 
11 Summary needed for interpretation of safety through Day 29
 
12 Updated to include additional potential intercurrent events
 
13 Removed as field is not collected in the eCRF

[figure not shown]
1 INTRODUCTION

The purpose of this document is to give details for the statistical analysis of study ICVX-12-202, a Phase 2, Randomized, Modified Double-Blind, Active Controlled Study to Characterize the Safety and Immunogenicity of IVX-A12, a RSV and hMPV VLP vaccine, in Adults 60 Years of Age and Older, supporting the clinical study report. The reader is referred to the CSP, CRF, and SIP for details of study conduct, data collection, and study integrity, respectively.

The terms study intervention, study vaccination, and study group are used throughout this SAP and refer to IVX-A12 and/or licensed RSV vaccine, AREXVY® (GSK Biologicals, Rixensart, Belgium).

The study groups and overall study design are described in Figure 1.

Figure 1 Study Design

2 CHANGES TO PROTOCOL PLANNED ANALYSES

The description for the Immunogenicity analysis set is further specified to target the intended study population.

3 DATA ANALYSIS CONSIDERATIONS

3.1 Sample Size Determination

Approximately 140 participants will be randomized 1:1 to IVX-A12 or AREXVY. Because all analyses will be descriptive in nature and no hypothesis is being tested statistically, no formal sample size calculations were performed. The sample size is considered sufficient for an assessment of immunogenicity and safety. For RSV A, an exploratory GMC ratio of 0.9, the 95% CI will be 0.57 to 1.42. A [REDACTED] standard deviation (SD) of [REDACTED] was assumed for RSV A, based on data reported by previous IVX-A12 Phase 1 and 2 studies. No replacement will be made for participants who withdraw from the study.

Table 1 Confidence intervals for assumed sample sizes and GMC ratios

NI Margin: 0.67		GMC ratio = 0.9		GMC ratio = 1.0	
Total N		95% CI	80% CI	95% CI	80% CI
100		0.52, 1.55	0.63, 1.28	0.58, 1.72	0.70, 1.42
140		0.57, 1.42	0.67, 1.21	0.63, 1.58	0.74, 1.35
180		0.60, 1.34	0.69, 1.17	0.67, 1.50	0.77, 1.30

3.2 Timing of Analyses

- The Primary Analysis will be performed after all participants have completed Day 29 (Visit 3) safety assessments and when all Day 29 primary immunogenicity data for RSV A (GFP RSV A MN Assay, [REDACTED]) are available. This analysis will support further evaluation of immunogenicity and safety of IVX-A12 in older adults. In addition, all available safety and immunogenicity data for RSV B (GFP RSV B MN Assay, [REDACTED], RSV A and RSV B MN Assays ([REDACTED]), and hMPV A and hMPV B (hMPV MN Assays, [REDACTED]) at the time of the primary analysis will be summarized as exploratory analyses.
- The Final Analysis will be performed after all participants have completed Day 181 (Visit 4) or terminate early from the trial and all data are available.

3.3 Analysis Populations

The following populations are defined (Table 2):

Table 2 Populations for Analysis

Population/analysis set	Description
Safety analysis set (SAF)	All randomized participants who receive study intervention, irrespective of their protocol adherence and continued participation in the study.

Table 2 **Populations for Analysis**

Population/analysis set	Description
	
Participants who withdraw consent to participate in the study will be included up to the date of their study withdrawal. Participants will be classified according to the study intervention they actually received.
 
The SAF is to be used for safety analyses.

Immunogenicity analysis set (IAS)	
All participants in the SAF who have no important protocol deviations judged to have the potential to interfere with the generation or interpretation of an immune response and have baseline and at least one post-baseline immunogenicity samples collected. Participants will be classified according to the study intervention they actually received.
 
The IAS is to be used for the analysis of immunogenicity endpoints.

In addition to the analysis sets defined above, summaries of participant disposition and participants not randomized will be performed in a Screened set, including all participants who have provided informed consent.

3.4 General Considerations

Data will be provided in data listings sorted by vaccination group and participant number. Tabular summaries will be presented by vaccination group and overall. Vaccination group will be defined as the actual vaccination received by a randomized participant.

Categorical variables will be summarized using frequency and percentages, where the denominator for calculation is the underlying analysis set population, unless otherwise stated. Continuous variables will be summarized with descriptive statistics of number of available observations, mean, standard deviation, median, minimum, maximum, and quartiles where appropriate.

All point estimates will be presented with a two-sided 95% CI, unless otherwise stated. For subgroup analyses, CIs will be presented for subgroup categories which have at least 5 evaluable participants per vaccination group.

The RSV nAb responses are measured as concentrations in IU/mL and therefore the geometric mean responses will be referred to as GMCs while the hMPV nAb responses are measured as titers (1/dilution) and the geometric mean responses will be referred to as GMTs. The GMCs and GMTs are referred to generally as geometric mean responses.

Immunogenicity summaries involving the Day 29 endpoint will include participants in the immunogenicity analysis set with a non-missing baseline and a non-missing result at Day 29.

For immunogenicity summaries involving data through Day 181, evaluable participants will be those in the immunogenicity analysis set with non-missing baseline and at least one non-missing post-baseline (Day 29 or 181) result.

Immunogenicity results below the LLoQ will be imputed to half of the LLoQ and results above the ULoQ will be imputed to the ULoQ prior to computing geometric mean responses. Responses will be imputed before any model-adjustment is performed.

The data analyses will be conducted using the SAS® System version 9.4 or above (SAS Institute Inc., Cary, NC). All SAS® programs used to generate analytical results will be developed and validated according to AstraZeneca programming standards and validation procedures.

3.4.1 General Study Level Definitions

Baseline

Baseline for immunogenicity endpoints is defined as the last non-missing result on the day of receiving study vaccination. Samples taken on the day of vaccination will be considered as evaluable for baseline, regardless of whether samples were drawn post-vaccination. If there is no value prior to or on the day of study vaccination, the baseline value will not be imputed and will be set to missing.

Baseline Tertiles

Baseline tertiles are defined as follows: first tertile is $\leq 33.3^{\text{rd}}$ percentile, second tertile is $> 33.3^{\text{rd}} - \leq 66.7^{\text{th}}$ percentile, and third tertile is $> 66.7^{\text{th}}$ percentile. Tertiles will be derived for each neutralization assay, across both study groups.

Study Groups

For the primary and final analyses, the study groups will be displayed in summaries as follows:

- IVX-A12 (RSV + hMPV)
- AREXVY (RSV)

Study Day

Study Day is defined as (date of assessment – date of study vaccination) + 1. Thus, the day of study vaccination will be study Day 1. There is no study Day 0.

Geometric Mean Concentration/Titer

Geometric mean concentrations/titers (GMCs/GMTs) will be calculated as the anti-logarithm $\Sigma(\log_2 \text{transformed response}/n)$, ie, as the anti-logarithm transformation of the mean of the

log₂-transformed response, where n is the number of participants with non-missing response information.

The CI for the GMC/GMT is calculated as the anti-logarithm transformation of the upper and lower limits of the two-sided 95% CI for the mean of the log₂-transformed responses.

Geometric Mean Concentration/Titer Ratio

The GMC/GMT ratio will be calculated as the geometric mean of the post-baseline response for IVX-A12 divided by the geometric mean of the post-baseline titer for AREXVY. The denominator for each geometric mean response is the number of participants with non-missing post-baseline response information.

The CI for the GMC/GMT ratio is calculated as the anti-logarithm transformation of the upper and lower limits of the two-sided 95% CI for the difference in means of the log₂-transformed responses.

Geometric Mean Fold Rise

The geometric mean fold rise (GMFR) is calculated as the geometric mean of the ratios of the individual post-baseline response value to the baseline response value (fold-rise). The GMFR will be calculated as the anti-logarithm of $\Sigma(\log_2 \text{transformed (post-baseline response/baseline response)}/n)$, where n is the number of participants with non-missing response information at baseline and at the post-baseline timepoint.

The CI for the GMFR will be calculated as described for the GMC/GMT.

Seroresponse

Seroresponse is a binary outcome where a success is defined as a fold-rise ≥ 4 . The CI for the proportion of participants with a seroresponse is calculated using the Clopper-Pearson exact method. In the event of 0% or 100% seroresponse, a one-sided 97.5% CI will be reported.

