1.3 Schedule of Activities

Table 1 Schedule of Activities

Procedure	Vaccination and Follow-up Period				Details in Protocol Section or Appendix
Visit number	1	2	3	4	
Visit Day (window) days	1 (N/A)	8 (+2)	29 (+3)	181 (± 14)	
Visit type	Clinic	Clinic	Clinic	Clinic	
Informed consent ^a	X (pre-dose)				Section 5.1
Demography and Medical history	X (pre-dose)				Sections 5.1 and 5.2
Targeted physical examination based on medical history	X (pre-dose)				Section 8.3.1
Height, Weight	X (pre-dose)				Section 8.3.2
Body temperature, Blood pressure	X (pre-dose)				Section 8.3.2
Verify eligibility criteria	X (pre-dose)				Sections 5.1 and 5.2
Randomization	X (pre-dose)				Section 6.3
Immunogenicity serum sample	X (pre-dose)		X	X	Section 8.9.1
Blood sample for cell-mediated immune responses	X (pre-dose)	X	X	X	Section 8.9.2
Vaccine administration	X				Sections 6.1 and 6.2
Immediate post-vaccination assessment ^b	X				Section 8.3.5.1
eDiary distribution and training for solicited ARs	X				Section 8.4.6
Solicited ARs ^c	X (ongoing through Day 8)				Section 8.4.6
eDiary collection		X			Section 8.4.6
Unsolicited AEs	X				Section 8.4.1 and 8.4.2
SAEs/AESIs/MAAEs	X				Section 8.4.1, 8.4.2, 8.4.7, 8.4.8, and 8.4.10
Concomitant medications ^d	X				Section 6.9

^a Confirm consent form signed prior to any procedures.

^b Immediate unsolicited AEs to be collected during the 30-minute observation period following vaccination.

^c Predefined solicited ARs recorded by participant in eDiary to assess reactogenicity. Investigators are to follow-up on any solicited ARs that are ongoing at Day 8 through to their resolution (see [Sections 8.4.6 and 9.4.3](#)).

^d All concomitant medications will be recorded in the source documents. Prohibited medications and any medications used to treat SAEs or AESIs will also be recorded in the eCRF.

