5.2 Exclusion Criteria

Participants are excluded from the study if any of the following criteria apply:

Medical Conditions

1. Acute (time-limited) or febrile (temperature $\geq 38.0^{\circ}\text{C}$ [100.4°F]) illness/infection within 3 days of planned dosing; participants excluded for transient acute illness may be dosed if illness resolves.
2. History of a clinically significant bleeding disorder (eg, factor deficiency, coagulopathy, or platelet disorder), or prior history of significant bleeding or bruising following IM injections or venipuncture.
3. History of hypersensitivity to any component of the study vaccination.
4. History of severe adverse reaction associated with a vaccine and/or severe allergic reaction (eg, anaphylaxis).
5. Known or suspected congenital or acquired immunodeficiency.
6. Known or suspected autoimmune condition as determined by history and/or physical examination.
7. History of Guillain-Barré syndrome or any other demyelinating condition.
8. History of malignancy other than treated non-melanoma skin cancers or locally-treated cervical cancer in previous 5 years.
9. Any condition that may significantly increase the risk to the participant because of participation in the study, impact the participant's ability to participate in the study, or impair the interpretation of the study data.

Prior/Concomitant Therapy

10. Receipt of any licensed or investigational RSV and/or hMPV vaccine any time prior to administration of study intervention.
11. Receipt of any licensed vaccine (other than licensed influenza or COVID-19 vaccines) within 28 days prior to or expected receipt within 28 days after administration of study intervention. Licensed influenza or COVID-19 vaccines are permitted beginning >14 days prior to and >14 days after administration of study intervention
12. Receipt of immunoglobulin or blood products within 3 months prior to administration of study intervention or expected receipt during the study.
13. Receipt of immune-modifying drugs or immunosuppressive therapy, such as anti-cancer chemotherapy or radiation therapy within 6 months prior to enrollment (or expected receipt during study), or long-term systemic corticosteroid therapy (prednisolone or equivalent at a dose of ≥ 20 mg daily or every other day for more than 2 consecutive weeks) within 6 months prior to study intervention or anticipated receipt during study. Topical/inhaled steroids or short-term oral steroids are permitted.

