3.4.2 Visit Window

A windowing convention will be used to determine the assignment of immunogenicity laboratory assessments to a nominal study visit for analyses summarized by visit. Samples collected outside of the analysis visit windows defined in Table 3 will be excluded from by-visit analyses.

Table 3 Analysis Visit Windows for Immunogenicity Data

Visit Description	Visit Number	CSP Visit Window		Analysis Visit Window	
		Days Relative to Visit	Study Day	Days Relative to Visit	Study Day
Baseline	1	≤ 1	1	≤ 1	1

Visit Description	Visit Number	CSP Visit Window		Analysis Visit Window	
		Days Relative to Visit	Study Day	Days Relative to Visit	Study Day
Day 29 post-vaccination	3	+3	29-32	±5	24-34
Day 181 post-vaccination	4	±14	167-195	Same as CSP Visit Window	

In the event of multiple assessments within a single analysis visit window, then the following rules will be applied:

- If there are two or more observations within the same visit window, then the non-missing observation closest to the scheduled visit will be used in the analysis;
- If two observations are equidistant from the scheduled visit, then the non-missing observation with the earlier collection date will be used in the analysis;
- If two observations are collected on the same day, then the non-missing observation with the earlier collection time will be included in the analysis. If the collection time is not available, the scheduled assessment will be favored over the unscheduled assessment.

If a visit window does not contain any observations, then the data will remain missing.

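### The SAP has two conflicting rules for choosing the baseline antibody result when a participant has two results on Day 1, and one of them can prefer a post-dose sample to a valid pre-dose sample

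*SAP*

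**What the plan says.** **SAP 3.4.1, Baseline.** The definition reads "Baseline for immunogenicity endpoints is defined as the last non-missing result on the day of receiving study vaccination". It continues: "Samples taken on the day of vaccination will be considered as evaluable for baseline, regardless of whether samples were drawn post-vaccination". The paragraph closes with the rule under which an absent baseline stays missing; it begins "If there is no value prior to or on the day of study vaccination, the baseline value will not be imputed and will be set".

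**SAP 3.4.2, Visit Window.** Table 3 has a Baseline row, "Baseline 1 ≤ 1 1 ≤ 1 1": at most 1 under days relative to visit and 1 under study day, for both the protocol and the analysis window. The tie-breaks are introduced by "In the event of multiple assessments within a single analysis visit window, then the following rules will be applied", with no exemption for Baseline. The same-day rule is: "If two observations are collected on the same day, then the non-missing observation with the earlier collection time will be included in the analysis". Where no collection time was recorded, the scheduled assessment is favored over the unscheduled one.

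**Protocol.** The Schedule of Activities (1.3) has the row "Immunogenicity serum sample X (pre-dose) X X", so the Visit 1 serum sample is to be taken before dosing. Section 9.4.2.1 defines fold rise as the post-dose titer over the pre-dose titer.

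**SAP Section 2**, which records changes to the protocol's planned analyses, mentions only the description of the immunogenicity analysis set.

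**The concern.** Two sections of one SAP tell the programmer to do opposite things with the same data: one takes the last Day 1 result, the other the earlier. The 3.4.1 rule can also put a sample drawn after the injection in place of a proper pre-dose one, and no reason is given.

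The baseline value is used in several places: fold rise and seroresponse (SAP 3.4.1), the log 2 baseline covariate in the Day 29 ANCOVA (4.2.1.5) and the later MMRM (4.2.3.2), and the baseline tertiles (3.4.1 and 4.2.1.8). Whether a baseline exists also decides Day 29 evaluability (3.4 and 4.2.1.1). The bar and line plots in 4.2.1.5 show baseline next to Day 29. If the plots follow the window rules and the model follows 3.4.1, the two could use different baselines for one participant.

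What is at stake is reproducibility and agreement with the protocol. The documents give no reason to expect a large bias.

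**Working it through.** The plan states no figure on this point, so there is none to reproduce. The check sets the rules side by side and then gives the scale under assumed inputs.

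**Step 1. Apply both rules to each Day 1 pattern.**

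| Results available | SAP 3.4.1 | SAP 3.4.2 | Agree? |
|---|---|---|---|
| One pre-dose result | that result | that result | yes |
| One post-dose result only | that result | that result | yes |
| Pre-dose sample without a result, post-dose with one | post-dose | post-dose | yes |
| Two pre-dose results | later | earlier | no |
| One pre-dose and one post-dose result | post-dose | pre-dose | no |
| Two post-dose results | later | earlier | no |

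The rules conflict only when there are two non-missing Day 1 results. Only in the fifth pattern does 3.4.1 set aside a valid pre-dose value in favor of a post-dose one.

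**Step 2. Samples from before Day 1.** Two pieces of text leave them out: the definition, which is limited to the day of vaccination, and the study-day entry of 1 in Table 3. Two others suggest that they count: the missing-baseline sentence, which refers to values before or on that day, and the entry of at most 1 in the same row of Table 3. The text supports either reading.

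**Step 3. Effect on the group's geometric mean fold rise (GMFR).** If k of n participants have their baseline multiplied by f, the GMFR is multiplied by f^(−k/n). Take n = 70 per group (140 randomized 1:1, SAP 3.1). The values of k and f are assumptions, since the documents give neither.

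- k = 1, f = 1.1: 1.1^(−1/70) = 0.9986
- k = 4, f = 1.25: 1.25^(−4/70) = 0.987
- k = 7, f = 2: 2^(−7/70) = 0.933

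**Step 4. Effect on seroresponse.** The threshold is a fold rise of at least 4. If a participant's two Day 1 results differ by a factor d (assumed), the class can change with the choice of baseline when the fold rise lies between about 4/d and 4 × d.

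- d = 1.1: 4/1.1 = 3.64 to 4 × 1.1 = 4.4
- d = 1.5: 4/1.5 = 2.67 to 4 × 1.5 = 6.0
- d = 2: 4/2 = 2.0 to 4 × 2 = 8.0

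This shows only that one participant's class could change. It says nothing about how often that happens or in which direction.

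**The case against.** **The trigger is rare by design.** One serum sample for immunogenicity is scheduled at Visit 1, before dosing, at the same visit as consent, randomization and vaccination. Protocol Section 8 allows repeat samples for safety reasons or technical issues. Where a repeat replaces a sample that gave no result, the two rules agree (third row of the table). This stands, and it keeps the point small.

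**Accepting a post-dose Day 1 sample is an explicit, prespecified choice.** This also stands. As a fallback it can be defended and it keeps participants in the analysis. What lacks a reason is preferring such a sample when a pre-dose result exists.

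**The specific definition should override the general window rule.** A programmer may well assume so, but the SAP does not say it, and Baseline is listed in the table that the window rules govern.

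Three stronger readings are tempting, and the documents do not support them:

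- *Earlier-day pre-dose samples are excluded outright and their participants dropped.* The missing-baseline sentence and the entry of at most 1 in Table 3 point the other way. The handling is inconsistent, not a clear exclusion.
- *Deferred dosing will produce such samples.* Protocol 5.2 says "participants excluded for transient acute illness may be dosed if illness resolves", and 5.5 provides for pausing vaccine administration. Neither says that serum has been drawn before the delay.
- *A participant without a baseline is lost to every primary measure.* The primary safety endpoints use the safety analysis set and need no baseline titer. Only the immunogenicity measures are lost.

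**Conclusion.** The point holds as a defect of wording. For two non-missing Day 1 results, SAP 3.4.1 and 3.4.2 select different baselines and no precedence is given. Applied literally, 3.4.1 can prefer a post-dose sample to a valid pre-dose one, contrary to the protocol's pre-dose sample and its definition of fold rise, and SAP Section 2 does not record this as a change. Whether samples from before Day 1 count is unclear.

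The effect should be small. Under the assumed inputs the GMFR multiplier runs from 0.9986 (one participant in 70, 1.1-fold) to 0.933 (seven in 70, 2-fold), and the second case would need many more duplicate or post-dose samples than the schedule leads one to expect. The documents give neither the frequency of such samples nor the difference between paired Day 1 results, so these figures show scale only. They are not evidence of bias. The change is worth making because it is cheap and removes a choice that would otherwise be left to programming.

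**What to change.** Replace the Baseline paragraph in SAP 3.4.1 with a rule in this order:

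1. Baseline is the last non-missing result from a sample collected before vaccination, on Day 1 or on an earlier day within a stated limit. The sponsor should set the limit, so that an old sample, for example from an initial screening, cannot serve.
2. If there is none, use the earliest Day 1 sample collected after vaccination and identify it in the listings.
3. If the collection time or the dosing time is missing, favor the scheduled pre-dose assessment, in line with what 3.4.2 already does when collection time is unavailable. This step is needed because Protocol 6.5 records dosing time only where applicable.
4. If none of these yields a result, baseline is missing and is not imputed.

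State that this rule overrides the 3.4.2 tie-breaks for the Baseline row. Align the entries in that row of Table 3, and the missing-baseline sentence, with the rule.

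The cost is SAP wording and a small programming change. No new data are collected, and the post-dose fallback means that no participant whom the current definition keeps is lost. The rule should be settled before treatment codes are broken for the analysis, because it affects who is evaluable.
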